## 9. TREATMENT OF SUBJECTS

### 9.1. Description of Study Drug

**Table 4: Investigational Product**

	Investigational Product
Product Name:	ST266 [Amnion-derived Cellular Cytokine Solution (ACCS)]
Dosage Form:	Liquid to be applied by pipette
Unit Dose	20 µL/tooth
Route of Administration	Topical application directly to the marginal gingiva
Physical Description	Clear to slightly yellow liquid that is free of particulates
Manufacturer	Stemnion, Inc.

### 9.2. Concomitant Medications

Use of concomitant treatment must be recorded in the subject's medical record and the electronic case report form (eCRF), including treatment/drug name, dose, indication, and start/stop dates. In addition, no homeopathic remedies (such as treatment with coconut oil) may be used during the study.

### 9.3. Treatment Compliance

Every treatment application of study drug will be performed in the dental clinic by the clinician/investigator (dental professional); therefore, non-compliance can be assessed easily by the investigator.

Treatments that are missed may be completed if done within the number of days indicated in [Table 5](#) from the original scheduled date.

Subjects who miss 20% or more of their prescribed treatments will be considered non-compliant and excluded from the per-protocol statistical analysis.

**Table 5: Treatment Windows by Group (+/- Days)**

	Visit Day									
Groups 1, 3	≤12	22	30	60	90	120	150	180	210	240
	N/A	3	3	3	5	7	7	7	7	7
Group 2	≤ 90					120	150	180	210	240
	N/A					7	7	7	7	7

#### **9.4. Randomization and Blinding**

A randomization scheme will be generated via interactive web response system (IWRS). Subjects will be randomized at the site after SRP is complete. Randomization will be stratified by site and smoker status (never smoked or quit smoking more than two years ago vs. has smoked within the last two years). Randomization will be blocked such that assignment to treatment groups both within sites and within smoker status will be approximately even (1:1:1). Any subjects that are discontinued after randomization and prior to treatment may be replaced. Examiners will be blinded to the treatment assignment.

A list of all subjects who have been treated will be maintained at the trial site, including each subject's identity, date of enrollment, and corresponding subject ID, so that any subject may be identified if required for any reason. The list is kept by the clinical site and must not be available to the sponsor. The electronic data collection system (EDC) will assign a screening ID number when a subject's data is entered at the screening visit. The subject will be identified only by that number until he/she is either randomized or withdrawn from the study. Upon randomization, the subject's screening ID number will be converted to a randomization ID number. Subjects will be identified only by either the screening ID number or the randomization number.

Treatment assignments will be blinded to the examiner, treatment administrator, and the subjects. Only in case of medical emergency or occurrence of AEs that warrant unblinding in the opinion of the Medical Monitor, will the treatment assignment be unblinded and made available to the investigator and the Medical Monitor. In the event of study unblinding, a non-study statistician will be assigned as the "unblinded statistician" to assist in unblinding and any safety review.

If the investigator feels it is necessary to unblind a subject's treatment assignment after an emergency situation, the investigator should contact the Medical Monitor or designee. Only after consultation with the Medical Monitor will a decision be made as to whether the treatment for the subject should be unblinded. The treatment assignment will be revealed on a subject-by-subject basis, thus leaving the blinding on the remaining subjects intact.

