## **7. INVESTIGATIONAL PLAN**

### **7.1. Overall Study Design**

The study is a 9-month, randomized, double-blind, placebo-controlled, parallel-design study of subjects with existing moderate to severe periodontal disease. The study design and duration is similar to the study design with previous compounds, e.g. Minocycline Microspheres, chlorhexidine chip, and others. Subjects will be recruited at multiple treatment sites. All subjects will be treated by a dental professional at the study site. The dental professional will be a qualified and trained licensed periodontist, dentist, or dental hygienist skilled in periodontal clinical research. All investigators will be trained in grading clinical parameters in the same manner for consistency. After signing informed consent, subjects will be screened with a medical and dental history and full mouth dental examination. Clinical parameters will be recorded including PD, CAL, and BOP. Subjects will have urinalysis in addition to blood tests including hematology and chemistry (liver and kidney function) panels. Women of child-bearing potential will be administered a pregnancy test.

If inclusion/exclusion criteria are met, subjects will undergo a baseline visit with measurements of FMPI, collection of gingival crevicular fluid (GCF), and blood samples. Subgingival plaque samples will be collected for microbial analysis. Vertical bitewing X-rays will be collected to assess RBL. Subjects will undergo SRP procedure(s) prior to being randomly assigned to 1 of 3 treatment groups indicated in Section 7.3. Local anesthesia must be used for SRP. All treatments of ST266 or placebo will be administered in office by a dental professional.

All subjects will be evaluated at screening, baseline, and Days 1, 15, 30, 60, 90, 180, and 270. Evaluations will be performed by a blinded dental professional to mask the group as all groups do not have the same study schedule. The blinded examiners will be independent from the dental professionals who apply the study drug to the subjects, thereby ensuring that the treatment assignment cannot be inferred based on the treatment schedule.

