## 7.3. Treatment Assignment

Group 1: ST266 dosed daily on Days 1-5, 8-12, 22, and 30 and then monthly for 7 months (Days 60, 90, 120, 150, 180, 210, and 240).

Group 2: ST266 dosed 2x/week (with at least one day between treatments) for the first 3 months and monthly for 5 months thereafter (Days 120, 150, 180, 210, and 240).

Group 3: Placebo dosed at the same frequency as Group 1.

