#### **9.5. Treatment Visits**

Treatment visits will consist of a review of the subject's medical and dental history, including recording concomitant medications. Additionally, the study medication will be applied to the buccal and lingual surfaces of the teeth. Following the application of the study medication an assessment of AEs will be performed. Subjects will be given oral hygiene instructions prior to the end of the visit.

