8.3.1 Primary Efficacy Analyses

The generalized estimating equations (GEE) method with a linear link and exchangeable covariance matrix (within subject correlation structure) will be used to estimate the treatment group effects with respect to change from baseline PD at 270 days, adjusted for baseline PD in tooth-sites with baseline PD ≥ 6 mm. The two primary hypotheses to be tested are:

- 1) The change in PD from baseline (PD ≥ 6 mm) (Screening Visit) at the 270 Day Visit differs between the Group 1 (see section 2.4) and Group 3 (placebo) treatments. Point estimates and 95% confidence intervals will be presented for the

treatment group differences in PD change from baseline at Day 270 by baseline smoker status.;

- 2) The change in PD from baseline (PD ≥ 6 mm) (Screening Visit) at the 270 Day Visit differs between the Group 2 (see section 2.4) and Group 3 (placebo) treatments. Point estimates and 95% confidence intervals will be presented for the treatment group differences in PD change from baseline at Day 270 by baseline smoker status.

SAS code for the GEE model is as follows:

```
proc gee data=Day270dataset
  where (base $\geq$ 6 and ITT Set='Y' and paramcd='PDEPTH');
  class subjid trt01a site smoker_status;
  model chg = trt01a base site smoker_status smoker_status*trt01a;
  repeated sub=subjid /type=exch;
  lsmeans trt01a/pdiff;
run;
```

Where:

- 1) The Day270dataset only includes records for Day 270 visit)
- 2) chg = change from baseline of each individual tooth site
- 3) (base \geq 6 and ittf1='Y' and paramcd='PDEPTH'): subsets the dataset to include only PD outcomes, the ITT population, and tooth sites with baseline PD greater or equal to 6mm.
- 4) chg= change in PD from baseline
- 5) trt01a = treatment group
- 6) site=investigator institution rather than tooth site
- 7) base = baseline PD

The 15-, 30-, and 60-Day visits were not included in the primary statistical model since the tooth-sites at the earlier visits may still be healing from the effects of the SRP procedure with possible SRP-related gingival swelling affecting the PD measures.

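### Placebo is given only on the Group 1 schedule, so the stated blinding of the treatment administrator cannot hold for the Group 2 versus placebo primary comparison, and blinding of the subject may not hold either

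*Protocol*

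**What the plan says.** Protocol 9.4 makes a three-way blinding claim: "Treatment assignments will be blinded to the examiner, treatment administrator, and the subjects". The study title and the synopses in both documents call the trial double-blind, and SAP 2.2 repeats this.

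Protocol 7.3, the Protocol synopsis and SAP 2.4 set out the schedules:

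- The first ST266 arm is treated on ten of the first 12 days, then on two further days up to Day 30, then at seven monthly visits ending on Day 240.
- The second ST266 arm follows another pattern: "Group 2: ST266 dosed 2x/week (with at least one day between treatments) for the first 3 months and monthly for 5 months thereafter". Its monthly visits also end on Day 240.
- The placebo arm copies only the first of these patterns: "Group 3: Placebo dosed at the same frequency as Group 1".

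Protocol 7.1 recognises the mismatch and gives its remedy: "Evaluations will be performed by a blinded dental professional to mask the group as all groups do not have the same study schedule". The examiners are also kept separate from the staff who treat, a safeguard that SAP 2.2 carries as well.

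At treatment visits (Protocol 9.5), AEs are assessed after application, and "Subjects will be given oral hygiene instructions prior to the end of the visit".

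The second primary hypothesis in SAP 8.3.1 is that the change in PD "differs between the Group 2 (see section 2.4) and Group 3 (placebo) treatments". SAP 8.6 also pools both ST266 groups against placebo.

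**The concern.** The schedule itself reveals the assignment. No arm receives placebo twice weekly, and neither document describes sham visits or a schedule-matched placebo for Group 2. The claim in Protocol 9.4 is therefore wider than the design can deliver for one of the two primary comparisons.

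What is at stake is how a Group 2 result may be described and read. If the limit is not stated in advance, the study report will carry an unqualified double-blind label for a comparison in which the person applying the product knows it is active. Behaviour and retention could then differ between arms by routes that a blinded examiner does not close. Group 2 also has a different number of staff contacts, each with hygiene coaching. That would affect the comparison even if blinding were perfect, so it has to be kept apart from the blinding point.

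**Working it through.** **1. Who can infer what**

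| Person | Information available | Can Group 2 be identified? |
|---|---|---|
| Treatment administrator | Works to the group's schedule. Protocol 9.3, Table 5 sets windows separately for Groups 1 and 3 and for Group 2. Week 1 already differs (Days 1-5 daily versus twice weekly) | Yes, with certainty |
| Subject | Knows own schedule. Knowledge of the other arms depends on consent text that is not available | Only if told how schedules map to arms |
| Examiner | Separate from the staff who apply the product (Protocol 7.1) | Protected by design |

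On the schedule alone, the probability of active treatment is 100% on the twice-weekly schedule. On the Group 1/3 schedule it is 50%, because Groups 1 and 3 are allocated equally.

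**2. Treatment visits** (from the day lists in Protocol 7.3; 12 to 13 weeks assumed for the first 3 months)

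- Groups 1 and 3: 5 + 5 + 2 + 7 = 19.
- Group 2: 2 × 12 + 5 = 29, to 2 × 13 + 5 = 31.
- Excess in Group 2: 29 − 19 = 10, to 31 − 19 = 12.

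**3. Timing of the excess**

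| Period | Groups 1 and 3 | Group 2 |
|---|---|---|
| To Day 12 | 5 + 5 = 10 | about 4 |
| To Day 30 | 12 | about 8 to 9 |
| To Day 90 | 5 + 5 + 2 + 2 = 14 | about 24 to 26 |
| Days 120 to 240 | 5 | 5 |

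The excess by Day 90 is 24 − 14 = 10 to 26 − 14 = 12, which is all of it. From Day 120 the schedules are identical. The excess therefore ends 270 − 90 = 180 days before the primary assessment.

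**4. Hygiene-instruction contacts.** Protocol Table 3 and its footnote g also place instruction at evaluation visits, so treatment visits alone are the wrong denominator.

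- Groups 1 and 3: 19 + 5 (screening, baseline, one scaling and root planing visit, Day 15, Day 270) = 24.
- Group 2, if the Day 15, 30, 60 and 90 evaluations fall on dosing days (assumption): 29 + 4 = 33, to 31 + 4 = 35. This is 33/24 = +38% to 35/24 = +46%.
- Group 2, if all four evaluations fall on separate days: up to 35 + 4 = 39, or 39/24 = +63%.

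**5. The plan's own sample size, and an illustration**

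Inputs from Protocol 7.2: difference 0.5 mm, SD 0.7 mm, 0.025 per comparison, 85% power. Testing is two-sided (SAP 3).

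The normal approximation, n = 2 × [0.7 × (z₀.₉₈₇₅ + z₀.₈₅) / 0.5]², gives 42.1, rounded up to 43. The t-test version gives 43.4, rounded up to 44. The stated 44 reproduces, and nothing in this point changes it.

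For illustration only, let b be a bias in favour of Group 2 with no true effect. The standard error is 0.7 × √(2/44) = 0.149 mm, and the rejection rate is Φ(b/SE − z₀.₉₈₇₅) + Φ(−b/SE − z₀.₉₈₇₅).

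| Assumed bias b (mm) | Rejection rate |
|---|---|
| 0 | 2.5% |
| 0.05 | 3.3% |
| 0.10 | 6.0% |
| 0.20 | 18.4% |

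The bias values are assumptions. The documents give no figure for any such effect.

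**The case against.** The best defence is that the plan saw the unequal schedules and protected the measurement that matters. PD is read by an examiner who is blinded and independent of the applier. That stands, and direct measurement bias in the primary endpoint is limited. It does not make the Protocol 9.4 statement true for the administrator.

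Four stronger readings are tempting, and the documents do not support them.

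- **Every Group 2 subject is unblinded.** A subject would need to know that placebo is never given twice weekly. No available text says that subjects are told this.
- **Group 2 receives far more coaching, by about 63%.** For treatment visits this is only the upper end of the range. It ignores instruction at evaluation visits, and it hides that early contact is heavier in Groups 1 and 3 and that schedules match from Day 120. Unequal contact is also not evidence about blinding.
- **Differential AE reporting threatens the primary hypothesis.** That hypothesis concerns PD change. AE assessment by staff who can infer active drug, on more occasions, bears on the safety endpoint, which is descriptive and untested (SAP 9.1).
- **Group 1 versus Group 3 can be certified as double-blind.** Protocol 9.1 describes ST266 as clear to slightly yellow, while the placebo is commercial saline (Protocol 10.8). The available text describes no colour-matching or opaque delivery. Only the matching of schedules is established.

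**Conclusion.** The point holds in limited form. The blinding stated in Protocol 9.4 cannot hold for administrators treating Group 2, and it may not hold for Group 2 subjects. This affects one of the two primary comparisons and the Group 2 part of the pooled comparison. Group 1 versus Group 3 is not affected by the schedule.

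Alongside this there is a contact imbalance of about 10 to 12 treatment visits, all by Day 90, resting on 12 to 13 weeks of twice-weekly dosing. It would need stating even under perfect blinding.

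A reader might infer that a Group 2 benefit could not be credited to ST266 at all. The documents do not go that far. They give no size for a home-care, coaching or retention effect, and the examiner safeguard is real. What follows is a caveat on interpretation and a correction to a stated design property.

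**What to change.** - **Blinding statements.** Reconcile Protocol 9.4, the title and synopsis, and SAP 2.2 with Protocol 7.1 and 7.3. State that Group 2 versus Group 3, and the Group 2 part of the pooled comparison in SAP 8.6, is examiner-blind, is not blinded to the administrator, and is possibly not blinded to the subject. Describe Group 1 versus Group 3 as the schedule-matched comparison.
- **SAP 8.3.1.** State that the Group 2 versus Group 3 result will be interpreted with this limit and with the unequal number of contacts. Present it beside the full-mouth plaque index comparison already planned in SAP 8.3.4 for Days 90, 180 and 270. Call that a partial check only: the index is measured after randomisation, and finding no difference would not exclude bias.
- **Safety.** Carry the same caveat to Group 2 AE frequencies in SAP 9.3.

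The cost is wording, and it can be settled before database lock. The downside is a less favourable description of the Group 2 comparison. No schedule, dosing, visit or sample-size change is proposed.

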#### **9.5. Treatment Visits**

Treatment visits will consist of a review of the subject's medical and dental history, including recording concomitant medications. Additionally, the study medication will be applied to the buccal and lingual surfaces of the teeth. Following the application of the study medication an assessment of AEs will be performed. Subjects will be given oral hygiene instructions prior to the end of the visit.

## **10. STUDY DRUG MATERIALS AND MANAGEMENT**

### **10.1. Study Drug**

ST266 (ACCS) is a novel secretome derived from proprietary cells. ST266 is composed of a complex mixture of cytokines, growth factors, nucleic acids, and undefined cellular components produced by cultured amnion-derived multi-potent progenitor (AMP) Cells in Iscove's Modified Dulbecco's Medium (IMDM). It contains at least 75 cytokines and growth factors in very low or physiological concentrations and 2 proteins (0.5% human serum albumin and epidermal growth factor) that are added to support the growth of the cells.

### **10.2. Study Drug Packaging and Labeling**

ST266 will be provided to the clinical site in two container types: frozen in sterile, single-use glass vials and in refrigerated liquid form provided in single-use plastic ampoules. Eppendorf pipettes and sterile pipette tips to be used for topical application of ST266 will also be provided to the site. The dispensing vials and pipette tips are single-use and will not be re-used.

### **10.3. Study Drug Storage**

ST266 must be stored per container type.

- ST266 in single-use glass vials must be stored frozen ( $-20\pm 5^{\circ}\text{C}$ ) until the day of use.
- ST266 in single-use plastic ampoules must be stored refrigerated ( $2-8^{\circ}\text{C}$ ) until the day of use.

### **10.4. Study Drug Preparation**

The study staff assigned and trained for "product handling" will transfer ST266 to a 5 mL tube (RNase, DNase and pyrogen free) that is then provided to the dental clinic.

- ST266 in single-use glass vials must be thawed prior to dispensing 1.5 mL of ST266 to a 5 mL tube.
- ST266 contained in a single-use plastic ampoule is ready to use. Approximately,  $1.3\pm 0.2$  mL of ST266 is transferred to a 5 mL tube.

### **10.5. Administration**

In the dental clinic, the Eppendorf pipette with the sterile tip supplied by the sponsor will be filled with 1 mL of ST266. Twenty (20) microliters ( $10\ \mu\text{L}$  to buccal surfaces and  $10\ \mu\text{L}$  to lingual surfaces) of ST266 will be applied directly to each tooth at the gingival margin by the study clinician at each treatment visit. The total daily dose will be less than 1 mL.

### **10.6. Study Drug Accountability**

Used and unopened containers of study drug will be retained in the study pharmacy for drug reconciliation by study staff trained in product handling and accountability.

### **10.7. Study Drug Handling and Disposal**

Study drug must be handled with protective gloves and mask. Opened containers of study drug from the clinic will be disposed of onsite using the standard handling protocol for the clinic after drug accountability has been performed by the sponsor or its agents. Unopened containers of study drug will be returned to Stemnion after accountability is performed at the end of the study for each site.

### **10.8. Placebo**

Commercially available sterile saline (0.9% NaCl) will be supplied to the clinical site by the sponsor for use as the placebo (treatment for Group 3) for the study. Sterile saline is stored at room temperature as indicated by the packaging and is ready for use. Sterile saline will be applied in the same manner and in the same volume as the investigational product, ST266. Accountability, handling, and disposal procedures are the same as for the study drug.

## 11. ASSESSMENT OF EFFICACY

### 11.1. Criteria for Primary and Secondary Efficacy Endpoint Evaluations:

- a. Pocket Depth (PD): Periodontal pocket depth will be determined with a UNC-15 periodontal probe at 6 sites per tooth, and rounded to the next lower whole millimeter.
- b. Clinical Attachment Level (CAL): The measurement of the position of the soft tissue in relation to the cemento-enamel junction (CEJ) that is a fixed point, using probing depth and the distance from the gingival margin to the CEJ.
- c. Bleeding On Probing (BOP): Dichotomous score of 0 or 1 indicating whether the site bleeds upon probing is performed independently of the gingival index measurement. Bleeding on probing will be measured from the 6 sites of the tooth as a secondary periodontitis variable:

0 = No bleeding

1 = Bleeding within 15 seconds following probing

4 =  $\sim 10^6$  bacteria

5 =  $>10^6$  bacteria

c. Radiographic Bone Level (RBL): Up to four vertical bitewing x-ray radiographs will be obtained at baseline and Days 90 and 270. For each time point, a total of two (2) radiographs will be taken from each side of the mouth. Crestal bone levels will be measured in mm relative to the CEJ, and changes in bone levels at Days 90 and 270 will be calculated relative to the baseline measurement. This procedure will be standardized for all sites, and radiographs will be interpreted by a central reading center.

d. Full-mouth Plaque Index (FMPI, Turesky modification of Quigley-Hein): Disclosing solution will be applied to the teeth and then plaque will be measured at 6 sites of each tooth.

0 = No plaque

1 = Separate flecks of plaque at the cervical margin of the tooth.

2 = A thin continuous band of plaque (up to 1 mm) at the cervical margin of the tooth.

3 = A band of plaque wider than 1 mm but covering less than one-third of the crown of the tooth.

4 = Plaque covering at least one-third but less than two-thirds of the crown of the tooth.

5 = Plaque covering two-thirds or more of the crown of the tooth.

### **11.3. Standardization and Calibration of Procedures**

Clinical assessments of PD, CAL, and BOP will be used to assess the efficacy of the therapy. Radiographic procedures, GCF, FMPI, and microbial sampling will also be performed. All of these procedures are prone to technique-sensitive sources of variability and require standardization and/or calibration exercises to minimize measurement variability. Such training exercises at each site will occur prior to the start of screening at each respective site. A dedicated oral examiner at the primary clinical center will serve as the “gold standard” examiner for calibration sessions. Details of the training protocols are provided in the Clinical Procedures Manual.

